### 11.1.3. Demography

Age: Age at the reference activity, computed as the number of complete weeks between the date of birth and the reference activity.

Conversion of weight to kg: the following conversion rule is used:

Weight in Kilogram = weight in Pounds / 2.2

Weight in Kilogram = weight in ounces / 35.2

The result is rounded to 2 decimals.

Conversion of height to cm: the following conversion rule is used:

Height in Centimetres = Height in Feet \* 30.48

Height in Centimetres = Height in Inch \* 2.54

The result is rounded to the unit (i.e. no decimal).

Conversion of temperature to °C: the following conversion rule is used:

$$\text{Temperature in } ^\circ\text{Celsius} = ((\text{Temperature in } ^\circ\text{Fahrenheit} - 32) * 5) / 9$$

The result is rounded to 1 decimal.

#### 11.1.4. Immunogenicity

- For a given subject and given immunogenicity measurement, missing or non-evaluatable measurements will not be replaced.
- The Geometric Mean Concentrations (GMCs) calculations are performed by taking the anti-log of the mean of the log titre transformations. Antibody concentrations below the cut-off of the assay will be given an arbitrary value of half the cut-off of the assay for the purpose of GMC calculation. The cut-off value is defined by the laboratory before the analysis and is described in Section 5.7.3 of the protocol.
- A seronegative subject is a subject whose antibody concentration is below the cut-off value of the assay. A seropositive subject is a subject whose antibody concentration is greater than or equal to the cut-off value of the assay.
- The assay cut-off is the value under which there is no quantifiable result available. For an assay with a specific 'cut\_off', numerical immuno result is derived from a character field (rawres):
  - If rawres is 'NEG' or '-' or '(-)', numeric result= cut\_off/2,
  - if rawres is 'POS' or '+' or '(+)', numeric result = cut\_off,
  - if rawres is '< value' and value<=cut\_off, numeric result =cut\_off/2,
  - if rawres is '< value' and value>cut\_off, numeric result =value,
  - if rawres is '> value' and value<cut\_off, numeric result =cut\_off/2,
  - if rawres is '> value' and value>=cut\_off, numeric result =value,
  - if rawres is '<= value' or '>= value' and value<cut\_off, numeric result =cut\_off/2,
  - if rawres is '<= value' or '>= value' and value>=cut\_off, numeric result =value,
  - if rawres is a value < cut\_off, numeric result = cut\_off/2,
  - if rawres is a value >= cut\_off, numeric result = rawres,
  - if rawres is a value >= cut\_off, numeric result = rawres,
  - else numeric result is left blank.

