## 4. ENDPOINTS

### 4.1. Primary

- Evaluation of immunogenicity in terms of anti-RV antibody concentrations
  - Serum anti-RV IgA antibody concentrations expressed as GMCs 1-2 months after Dose 2 in each of the HRV liquid formulation groups (Liq\_A, Liq\_B and Liq\_C).
  - Anti-RV IgA antibody seroconversion rate\* 1-2 months after Dose 2 in the lyophilised and pooled liquid groups.
  - Serum anti-RV IgA antibody concentrations expressed as GMCs 1-2 months after Dose 2 in the lyophilised and pooled liquid groups.

\*Seroconversion rate is defined as the percentage of subjects who were initially seronegative (i.e., with anti-RV IgA antibody concentration < 20 U/mL prior the first dose of HRV vaccine) and developed anti-RV IgA antibody concentration  $\geq$  20 U/mL at Visit 3.

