**5.2.2. Elimination from Per-Protocol analysis Set (PPS)**

A subject will be excluded from the PPS analysis under the following conditions

Code	Decode => Condition under which the code is used
900	Questionable subject => subjects with invalid informed consent or fraudulent data
1030	Study vaccine dose not administrated but subject number allocated => subjects enrolled but not vaccinated
1040	Administration of vaccine(s) forbidden in the protocol => Administration of a vaccine not foreseen by the study protocol and administered during the period starting from 30 days before the first vaccination and ending at Visit 3, with the exception of the inactivated influenza vaccine, which is allowed at any time during the study, and other licensed routine childhood vaccinations.
1060	Randomisation code broken at the investigator site => Subjects unblinded in SBIR or unblinding reported as protocol deviation
1070	Study vaccine dose not administered according to protocol => 
 
• Subjects vaccinated with the correct vaccine but who regurgitated for one of the 2 doses;
 
• subjects for whom the second administered dose is not aligned with the first dose (e.g. lyo as second dose after a first dose with liquid from lot A; or liquid from lot B as second dose after a first dose with liquid from lot A)
 
• Subject who did not receive the second dose and return to visit 3 blood sample
 
• Subject who was given multiple doses at one visit
 
• Route of vaccination which is not oral
 

1080	Vaccine temperature deviation => Subjects who have received a vaccine which had a temperature deviation qualified as inappropriate for use by Quality Assurance.
1090	Expired vaccine administered => Subjects who received an expired vaccine

Code	Decode => Condition under which the code is used
2010	Protocol violation (inclusion/exclusion criteria) => Ineligible subjects who was vaccinated (i.e. Age at dose 1 is not between 42-90 days, gestational age is < 37 weeks 0 day or > 41 weeks 6 days or other eligibility criteria – see section 4.2 and 4.3 of the protocol)
2020	Initially seropositive or initially unknown antibody status => Anti-HRV concentration $\geq$ 20 U/mL or unknown at pre-dose 1 blood sample

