#### Immunogenicity:

- For a given subject and a given immunogenicity measurement time point, missing or non-evaluable measurements will not be replaced.

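### SAP 11.1.4 codes a result reported only as below some value above the cut-off as that value, so a Visit 3 sample that may be under 20 U/mL counts as seroconverted

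*SAP*

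**What the plan says.** Annex 1 of the SAP (section 11.1.4) lists how a character laboratory result is turned into a number. For an upper-bounded result above the cut-off the line reads: "if rawres is '< value' and value>cut\_off, numeric result =value". A combined line for '<= value' and '>= value' also assigns the value when it is at or above the cut-off, so '<=20' becomes 20. In the other direction: "if rawres is '> value' and value<cut\_off, numeric result =cut\_off/2". Both SAP versions carry these lines.

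The surrounding rules are:

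- Cut-off: 20 U/mL (Protocol, Table 7). Seroconversion requires a subject "with anti-RV IgA antibody concentration < 20 U/mL prior the first dose of HRV vaccine" who then reaches at least 20 U/mL at Visit 3 (SAP 4.1).
- Serostatus: "A seropositive subject is a subject whose antibody concentration is greater than or equal to the cut-off value of the assay" (SAP 11.1.4).
- Low results: "Antibody concentrations below the cut-off of the assay will be given an arbitrary value of half the cut-off", that is 10 U/mL (SAP 11.1.4).
- Missing data: "missing or non-evaluable measurements will not be replaced" (SAP 11.1.6).
- Per-protocol exclusions (SAP 5.2.2): code 2020 covers "Initially seropositive or initially unknown antibody status", at the pre-Dose 1 sample only. Code 2100 covers post-vaccination results that are not available. No code covers a Visit 3 result that exists but leaves serostatus undetermined.

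**The concern.** A result of '<40' says only that the concentration lies somewhere under 40. Replacing it by 40 picks the highest value compatible with the report and turns an undetermined serostatus into a positive one. At baseline this does no harm to the per-protocol set, because seropositive and unknown subjects are both removed. At Visit 3 nothing removes or flags the sample.

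All three co-primary criteria use Visit 3 values: the lot GMC ratios, the seroconversion difference (margin -10%) and the pooled GMC ratio (margin 0.67). The seroconversion criterion is the one to watch. An arm with more true negatives has more samples that can be wrongly turned positive, so a real deficit of the liquid vaccine could look smaller than it is. No count of such results and no sensitivity analysis for them is planned.

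**Working it through.** **1. The coded value against the reported result** (cut-off 20 U/mL).

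- '<40' is coded 40 and counted as seroconverted. This is right if the true value is 20 to 40 and wrong if it is below 20, where the SAP would otherwise code 10.
- '<=20' is coded 20 and counted as seroconverted. This is right only if the value is exactly 20.
- '<90' is coded 90 and counted as at least 90 U/mL. This is wrong for any true value.

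For every '< value' result the coded concentration exceeds the true one.

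**2. The plan's own figure.** Protocol Table 18 gives 99.5% power for the seroconversion comparison at 85% in both arms, 960 against 320 subjects. A Miettinen-Nurminen score calculation with one-sided 2.5% gives 99.6%. The sample-size figure is not in dispute.

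**3. Type I error at the margin.** Inputs: true rates 75% (liquid) and 85% (lyophilised), so the true difference is -10 points; n = 960 and 320. Assumption: a share f of all Visit 3 results in each arm is affected, and true status within that share follows the arm's rate. The documents give no value for f; 0.5% to 5% is shown.

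- Observed rate: p + f(1 - p).
- Observed difference: -0.10 + f(0.25 - 0.15) = -0.10 + 0.10f.
- Type I error: Phi((observed difference + 0.10)/SE - 1.96).

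At f = 1% the observed rates are 75.25% and 85.15%, the difference is -9.9 points, and SE = sqrt(0.7525 x 0.2475/960 + 0.8515 x 0.1485/320) = 0.0243. The error is Phi(0.001/0.0243 - 1.96) = 2.75%.

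| f | Observed difference (points) | One-sided type I error |
|---|---|---|
| 0 | -10.0 | 2.5% |
| 0.5% | -9.95 | 2.62% |
| 1% | -9.9 | 2.75% |
| 2% | -9.8 | 3.02% |
| 5% | -9.5 | 4.00% |

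**4. Dependence on the assumption.** These error rates come from simulating the score test, which gives 2.7% with no recoding.

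- Same absolute share of true negatives recoded in both arms: the difference does not move and the error stays at 2.7%.
- Same fraction of true negatives recoded, taken as 6.7% (1.7 points liquid, 1.0 point lyophilised): 5.0%.

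**5. GMC.** If all affected samples are truly negative and reported '<40', the group GMC is multiplied by 10^(f x log10(40/10)) = 4^f, which is 1.014 at f = 1% and 1.072 at f = 5%. An equal factor in each group cancels in a ratio. Under the model of step 3, the miscoded negatives alone move the liquid/lyophilised ratio by 10^(f x 0.10 x 0.602), about 0.14% at f = 1% and 0.7% at f = 5%.

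**6. Deletion as a remedy.** Take a true rate of 85% and f = 1%, all truly negative. The SAP rule gives 86.0%. Deleting the samples gives 85/0.99 = 85.86%. Most of the inflation (0.86 of 1.0 point) remains, because deletion removes low responders.

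**The case against.** The list is a generic derivation annex. It also maps 'POS' and '+' and repeats one line verbatim, so its presence does not show that this assay yields such results. The ELISA is quantitative, read from a standard curve (Protocol, Appendix A), and the SAP describes the cut-off as the limit of quantification, so a censored low result would normally be '<20' and be coded 10. About 0.7 mL of serum is collected for one antibody, so shortage is an unlikely trigger. The laboratory is blinded (Protocol 5.3), so a difference in handling between arms is not expected. The line for '> value' below the cut-off pushes results down, so the net direction of the whole list is unknown. All of this stands, and it limits the size of the effect. It does not make the coded value right when the line is used.

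Three stronger readings are tempting, and the documents do not support them:

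- **That the rule misclassifies serostatus every time.** A '<40' sample truly between 20 and 40 is classified correctly.
- **That inflated group levels necessarily favour non-inferiority.** Equal absolute recoding leaves the seroconversion difference unchanged, and equal factors cancel in the GMC ratios.
- **That the rule contradicts the SAP on non-evaluable results.** The SAP says "For a given subject and given immunogenicity measurement, missing or non-evaluatable measurements will not be replaced", but it does not define non-evaluable and gives these results an explicit rule. The conflict is arguable and the point does not need it.

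**Conclusion.** The line is wrong as a coding rule. Whenever it is applied to a '< value' result it records a concentration higher than the one reported. It calls the infant seroconverted without evidence, and for '<90' it contradicts the laboratory outright. No other provision in the protocol or SAP repairs this at Visit 3.

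The consequence for the trial is unquantified and may be nil, because no document gives the frequency of such results. If they occur, group GMCs are overstated, and seroconversion rates are overstated to the extent that true values lie below 20 U/mL. The comparison is affected only if recoding differs between arms or scales with true negatives. Under the moderate model of step 3 the error at the margin stays between 2.6% and 4.0% for f from 0.5% to 5%; the harsher assumption of step 4 gives 5.0%. These are illustrations of an assumed f, not estimates for this trial. A correction is justified because the rule feeds confirmatory endpoints and costs little to change before unblinding.

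**What to change.** In SAP 11.1.4:

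- Split the combined '<=' / '>=' line, so that '>= value' results at or above the cut-off keep their value.
- Do not assign the bound to '< value' above the cut-off or to '<= value' at or above it. Re-assay if serum remains; otherwise treat Visit 3 serostatus as unknown.
- Apply the same treatment to '> value' and '>= value' below the cut-off.
- Widen code 2100 in SAP 5.2.2, or add a code, to cover unknown status at Visit 3.
- For the endpoint of at least 90 U/mL, count a '< value' result with value up to 90 as not reaching it.

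Report the number of such results per group. If there are any, show the co-primary results with the affected subjects retained under both bounds (half the cut-off, and the value), since deletion alone removes likely low responders.

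The cost is a few lines of SAP text and derivation code. Any sample that cannot be resolved leaves the per-protocol set. If no such result occurs, the analysis is unchanged.

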#### 11.1.5. Safety

- For analysis of solicited, unsolicited adverse events (such as serious adverse events or adverse events by primary MedDRA term) and for the analysis of concomitant medications, all vaccinated subjects will be considered. Subjects who did not report the event or the concomitant medication will be considered as subjects without the event or the concomitant medication respectively.
- In case there will be more than 5% of subjects without documented dose for solicited symptoms (i.e., symptom screen not completed), sensitivity analysis will include only vaccinated subjects for doses with documented safety data (i.e., symptom screen completed).

- The following rules will be used for the analysis of solicited symptoms:
  - Subject who didn't document the presence or absence of a solicited symptom after one dose will be considered not having that symptom after that dose in the analysis done on "administrated dose"
  - Subjects who documented the absence of a solicited symptom after one dose will be considered not having that symptom after that dose.
  - Subjects who documented the presence of a solicited symptom and fully or partially recorded daily measurement over the solicited period will be included in the summaries at that dose and classified according to their maximum observed daily recording over the solicited period.
  - Subjects who documented the presence of a solicited symptom after one dose without having recorded any daily measurement will be considered as having that symptom after that dose).

- For the analysis, temperatures will be coded as follows for oral, axillary or tympanic route:

Grade	Temperature
0	< 38.0°C
1	≥ 38.0°C - < 38.5°C
2	> 38.5°C - < 39.5°C
3	> 39.5°C

- Note that for all tables described in this section, the way the percentage of subjects will be derived will depend on the event analysed (see table below for details). As a result, the N value will differ from one table to another.

Event	N used for deriving % per subject for Vaccination phase	N used for deriving % per dose for Vaccination phase
Concomitant vaccination	All subjects with study vaccine administered	All study visits with study vaccine administered
Solicited general symptom	Primary analysis: all subjects with study vaccine administered Sensitivity analysis as applicable (see section 6.4.2): all subjects with at least one solicited general symptom documented as either present or absent (i.e., symptom screen completed)	Primary analysis: all study visits with study vaccine administered Sensitivity analysis: all study visits with study vaccine administered and with at least one solicited general symptom documented as either present or absent (i.e., symptom screen completed)
Unsolicited symptom	All subjects with study vaccine administered	All study visits with study vaccine administered
Concomitant medication	All subjects with study vaccine administered	All study visits with study vaccine administered

For summaries by MedDRA primary preferred term combining solicited and unsolicited adverse events, solicited adverse events will be coded as per the following MedDRA codes

Solicited symptom	Lower level term code	Corresponding Lower level term decode
Fever	10016558	Fever
Irritability/Fussiness	10022998	Irritability
Diarrhoea	10012727	Diarrhoea
Vomiting	10047700	Vomiting
Loss of appetite	10003028	Appetite lost
Cough/runny nose	10011224	Cough

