**5.6.8. Assess pre-vaccination body temperature**

The oral/axillary/rectal body temperature of each subject needs to be measured prior to any study vaccine administration. If the subject has fever [fever is defined as temperature  $\geq 38.0^{\circ}\text{C}/100.4^{\circ}\text{F}$  regardless the location of measurement on the day of vaccination, the vaccination visit will be rescheduled within the allowed interval for this visit (see [Table 5](#)).

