**Table 11 Solicited general adverse events**

Fever
Irritability/Fussiness
Diarrhoea
Vomiting
Loss of appetite
Cough/runny nose

Note: Temperature will be recorded in the evening. Should additional temperature measurements be performed at other times of day, the highest temperature will be recorded in the eCRF. The temperature can be recorded by any age-appropriate route. The preferred route for recording temperature in this study will be oral, axillary or rectal.

**8.1.4. Clinical laboratory parameters and other abnormal assessments qualifying as adverse events or serious adverse events**

In absence of diagnosis, abnormal laboratory findings (e.g., clinical chemistry, haematology, urinalysis) or other abnormal assessments (e.g., vital signs etc) that are judged by the investigator to be clinically significant will be recorded as AE or SAE if they meet the definition of an AE or SAE (refer to Sections 8.1.1 and 8.1.2). Clinically significant abnormal laboratory findings or other abnormal assessments that are present at baseline and significantly worsen following the start of the study will also be reported as AEs or SAEs.

The investigator will exercise his or her medical and scientific judgement in deciding whether an abnormal laboratory finding or other abnormal assessment is clinically significant.

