#### 11.1.5. Safety

- For analysis of solicited, unsolicited adverse events (such as serious adverse events or adverse events by primary MedDRA term) and for the analysis of concomitant medications, all vaccinated subjects will be considered. Subjects who did not report the event or the concomitant medication will be considered as subjects without the event or the concomitant medication respectively.
- In case there will be more than 5% of subjects without documented dose for solicited symptoms (i.e., symptom screen not completed), sensitivity analysis will include only vaccinated subjects for doses with documented safety data (i.e., symptom screen completed).
- The following rules will be used for the analysis of solicited symptoms:
  - Subject who didn't document the presence or absence of a solicited symptom after one dose will be considered not having that symptom after that dose in the analysis done on "administrated dose"
  - Subjects who documented the absence of a solicited symptom after one dose will be considered not having that symptom after that dose.
  - Subjects who documented the presence of a solicited symptom and fully or partially recorded daily measurement over the solicited period will be included in the summaries at that dose and classified according to their maximum observed daily recording over the solicited period.

- Subjects who documented the presence of a solicited symptom after one dose without having recorded any daily measurement will be considered as having that symptom after that dose).
- For the analysis, temperatures will be coded as follows for oral, axillary or tympanic route:

Grade	Temperature
0	< 38.0°C
1	≥ 38.0°C - ≤ 38.5°C
2	> 38.5°C - ≤ 39.5°C
3	> 39.5°C

- Note that for all tables described in this section, the way the percentage of subjects will be derived will depend on the event analysed (see table below for details). As a result, the N value will differ from one table to another.

Event	N used for deriving % per subject for Vaccination phase	N used for deriving % per dose for Vaccination phase
Concomitant vaccination	All subjects with study vaccine administered	All study visits with study vaccine administered

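### Would the SAP's fever coding lose rectal temperatures, or readings of exactly 38.5 °C and 39.5 °C, from the fever results?

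*SAP*

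**What the plan says.** On route, both versions of the SAP open the coding rule in Section 11.1.5 with "For the analysis, temperatures will be coded as follows for oral, axillary or tympanic route". The note to protocol Table 11 reads "The preferred route for recording temperature in this study will be oral, axillary or rectal", and also says "The temperature can be recorded by any age-appropriate route". For the check before vaccination, protocol Section 5.6.8 applies the 38.0 °C threshold "regardless the location of measurement on the day of vaccination". Protocol Table 14, which grades solicited fever, mentions no route.

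On the bands, SAP Amendment 1 gives grade 1 as "≥ 38.0°C - < 38.5°C" and grade 2 as "> 38.5°C - < 39.5°C". In the first SAP version grade 2 is "> 38.5°C - ≤ 39.5°C", and grade 1 likewise includes its upper bound. Protocol Table 14 has the same closed upper bounds. All three start grade 3 above 39.5 °C and start fever at 38.0 °C. The document history in Amendment 1 declares one change, the gastroenteritis derivation in Section 6.4.2.

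**The concern.** Parents record a temperature for fever, not a grade (protocol Table 13), so the analyst's coding decides both whether fever was present and how severe it was. If the SAP table is read as applying only to the routes it names, rectal readings in these infants have no coding rule. Together with the rule that unreported symptoms count as absent, that suggests rectal fevers could drop out of the counts, most of all in countries where rectal measurement is common, and so distort the by-country summaries.

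The boundary signs raise a second worry. Temperatures converted from Fahrenheit are rounded to one decimal, so exact values of 38.5 and 39.5 °C will occur. Under the Amendment 1 bands they fit nowhere.

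Fever is a solicited symptom under a secondary objective, so a real loss of cases would matter for the reactogenicity profile.

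**Working it through.** **Boundary values.** Inputs: the bands in protocol Table 14, the bands in SAP Amendment 1 Section 11.1.5, and the conversion rule in SAP Section 11.1.3.

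| Grade | Protocol Table 14 and first SAP version | SAP Amendment 1 |
|---|---|---|
| 0 | T < 38.0 | T < 38.0 |
| 1 | 38.0 ≤ T ≤ 38.5 | 38.0 ≤ T < 38.5 |
| 2 | 38.5 < T ≤ 39.5 | 38.5 < T < 39.5 |
| 3 | T > 39.5 | T > 39.5 |

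Both sets of bands were applied to every 0.1 °C value from 35.0 to 42.0, which is (42.0 − 35.0)/0.1 + 1 = 71 values, 41 of them at or above 38.0.

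- Protocol bands: each of the 71 values gets exactly one grade.
- Amendment 1 bands: 69 values get the same grade as in the protocol. Two get none: 38.5 (protocol grade 1) and 39.5 (protocol grade 2).
- On the Fahrenheit scale, in 0.1 °F steps from 95.0 to 107.9, only two readings reach these values: (101.3 − 32) × 5/9 = 38.5 and (103.1 − 32) × 5/9 = 39.5.

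The next question is which planned displays depend on those two values.

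| Display | 38.5 °C | 39.5 °C |
|---|---|---|
| Any fever, ≥ 38.0 | counted | counted |
| Grade 3, > 39.5 | not counted, either version | not counted, either version |
| 0.5-degree summary (SAP 6.4.2) | in ≥ 38.0 only | in ≥ 38.0, > 38.5 and > 39 |

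The available solicited-symptom templates (19, 20, 21 and 28) show all fever, grade 3 fever and related fever. None splits grade 1 from grade 2. An even spread of fevers over 38.0 to 39.5 °C would put 2 of 16 values, about 12%, on a boundary, but that spread is only an assumption and the share affects no display in view.

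**Rectal readings.** The feared loss can be written as tabulated incidence = true incidence × (1 − r), where r is the share of rectal readings. The documents do not give r. With a true incidence of 25% per dose (Template 20 shows about 20% to 28%, in mock tables copied from ROTA-061):

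- r = 10%: 25% × 0.90 = 22.5%
- r = 30%: 25% × 0.70 = 17.5%
- r = 50%: 25% × 0.50 = 12.5%

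This formula holds only if every rectal fever is recoded as no fever. The rules in SAP Section 11.1.5 do not do that:

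1. Counting as absent applies to a subject who documented neither presence nor absence of the symptom. A recorded rectal temperature is documentation.
2. A subject with the symptom documented and at least some daily measurements is classified by the highest daily value.
3. A subject with the symptom documented and no daily measurement at all still counts as having it.

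The fever definition under protocol Table 13, the grades in Table 14 and the temperature summary in SAP Section 6.4.2 carry no route restriction. The SAP gives no rectal scale and no route adjustment. An analyst holding a rectal reading therefore has one scale available, Table 14. Under it, the implied loss is zero for any r.

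**The case for a change.** The strongest case for acting is that the route mismatch is not a misprint in one version: it stands in both SAP versions, and the protocol names rectal measurement repeatedly. Read literally, the coding table is specific to certain routes, and because it determines whether fever is present as well as its grade, a gap there would reach the overall and grade 3 fever rows, not just a boundary category. A rule set in advance should cover every route collected and give each value one grade. The departure from Table 14 is undeclared, since the Amendment 1 history does not mention it and SAP Section 9 reports no changes from the planned analyses.

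The inconsistency stands. The step from it to lost fevers does not: silence on a route is not an instruction to discard readings, and the protocol the SAP implements supplies the missing scale. Naming tympanic readings contradicts nothing either, since the protocol allows any suitable route. That the change of signs is undeclared argues for a slip rather than a decision, either a typing error or a ≤ lost in reading the PDF. Section 5.6.8 is weaker support than it seems, because it concerns deferring vaccination and not grading solicited fever. The by-country distortion has no data behind it, as route use by country is not given. Allocation is also minimised on centre and country (protocol Section 5.2.2.2.1), so national habits in measurement should be roughly balanced between groups.

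**Conclusion.** No change to the plan follows. The route list in SAP Section 11.1.5 is incomplete and the Amendment 1 signs disagree with protocol Table 14, but the first is a gap that analysts fill from Table 14 and the second is clerical. Two exact temperatures lack a grade 1 or grade 2 label. Counts of any fever and grade 3 fever and the 0.5-degree summary do not depend on the signs, and no recorded rectal fever is removed by any rule in the SAP. The figures of 22.5%, 17.5% and 12.5% are not consequences of the plan.

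The conclusion rests on two assumptions: that analysts apply the protocol's single scale to all recorded routes, and that no table outside the templates available separates grade 1 from grade 2 fever. If such a table existed, the closed bounds in Table 14 would settle both values. The analysis is descriptive, and no co-primary objective is touched.
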